1. AMENDMENT HISTORY

Amendment No.	Protocol Version No.	Date issued	Author(s) of changes	Details of Changes made

2. SYNOPSIS

Study Title	A retrospective observational analysis of a cohort with Heart Failure with Preserved Ejection Fraction from a BNP pathway clinic
Problem statement	Heart failure with preserved ejection fraction (HFpEF) is a complex condition with various causes that is not yet fully understood. Most significantly there is no single method of diagnosing or treating the condition. Recently a novel non-invasive diagnostic criterion to predict the likelihood of HFpEF was proposed by Reddy et al. (2018) called H2FPEF. The main limitation of this study was the use of a single centre population from the Mayo clinic in Rochester, US. Another limitation is that the H2FPEF diagnostic criterion consists of common and often co-existing conditions which could as a result overestimate HFpEF probability. The aim of the investigators is to retrospectively test the H2FPEF criteria on the population at Queen Alexandra Hospital (QAH) in Portsmouth, which is of a lower socio-economic status and greater ethnic diversity. Implications of the project if H2FPEF is proved to be generalizable to the population is that it can be used within the Trust and rolled out to others. This would allow diagnosis to be made quicker and more cost effectively using echocardiography and without the need for invasive cardiac catheterisation. On the other hand if H2FPEF is found not to be applicable to the population then further research would be required to find the ideal diagnostic tool.
Research question / hypothesis	The investigator's hypothesis is that when H2FPEF criteria is compared against retrospectively held data for the patient population at QAH that this will overestimate the probability of HFpEF
Study Design	The study is a single-centre retrospective observational analysis
Study Participants	Patients who attended heart failure clinics at Queen Alexandra Hospital between January 1st 2016 – December 31st 2016
Planned Sample Size	2000
Follow-up duration	1 year
Planned Study Period	04/10/2019 – 30/04/2020
Primary Objective	The primary objective of the investigator's project is to test if the H2FPEF score accurately predicts HFpEF on the population at Queen Alexandra Hospital.
Secondary Objectives	
 • Investigate if H2FPEF overestimates HFpEF diagnosis on the patient population when compared against known BNP levels. • To evaluate if H2FPEF can be validated on the patient population and be utilised to improve patient pathway for HFpEF. • To monitor patient responses to treatments and care for one year.
Primary Outcome Measure	To assess the predictive accuracy of H2FPEF at predicting HFpEF on the patient population as calculated by logistic regression, with diagnostic accuracy being assessed by sensitivity and specificity calculations.
Secondary Outcome Measures	
 • ANOVA will be performed to provide one simultaneous evaluation of the data to determine if there is a significant difference between

	H2FPEF score and diagnosis of HFpEF. •To assess number of hospital admissions and any changes in treatment/ care after one year for the population.
--	--

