HFpEF was previously characterised as ‘diastolic dysfunction’ but this terminology was changed as it was found that diastolic dysfunction was also seen in patients with ‘systolic dysfunction’ (Borlaug and Paulus, 2011). Myocardial stiffness which leads to increased filling pressures is a common pathophysiologic attribute of HFpEF despite its multifactorial aetiology (Telles and Marwick, 2018). Other common conditions associated with HFpEF include: atrial fibrillation (AF), chronotropic incompetence, pulmonary hypertension, right ventricular dysfunction and endothelial dysfunction; with common non-specific risk factors such as: age, gender, hypertension, obesity, diabetes, metabolic syndrome and renal failure (Borlaug, 2014; Ferrari et al., 2015; Harper et al., 2018). This complex heterogeneity of HFpEF which is not yet fully understood highlights the difficulty that clinicians have in being able to diagnose the condition.

Diagnosis of HFpEF is difficult and as of yet there is no test to confirm diagnosis, with current guidelines saying initial diagnosis should include the presence of typical signs and symptoms, an elevated B-type natriuretic peptide (BNP) (>35 pg/mL and/or N-Terminal pro-

B-type Natriuretic Peptide [NT-proBNP] >125 pg/mL) and ejection fraction $\geq 50\%$ (Lekavich et al., 2015; Ponikowski et al., 2016). Echocardiography is the preferred method of assessing for HFpEF due to it being widely available, non-invasive, and able to provide immediate results (Ponikowski et al., 2016). Recent studies comparing the use of echocardiography against 'gold standard' invasive cardiac catheterisation to assess cardiac filling pressures found echocardiography to be just as accurate and reliable (Anderson et al., 2017; Lancellotti et al., 2017). Implications of this research would be that patients could be assessed as outpatients by focus echocardiography rather than invasively in the cardiac catheterisation lab, which would improve patient experience, enhance patient outcomes and prove cost-effective for trusts.

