8.2 Primary and Secondary Outcome Measures

Primary outcome measure

- Accuracy of H2FPEF at predicting HFpEF on the patient population will be assessed as specificity and sensitivity as calculated by logistic regression

Secondary outcome measure

- Investigate if H2FPEF overestimates HFpEF diagnosis on the patient population when compared against known BNP levels.
- To evaluate if H2FPEF can be validated on the patient population and be utilised to improve patient pathway for HFpEF.
- To assess patient outcomes after one year, including any changes in medication or treatment as well as number of hospital admissions and reported symptoms.

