9. STUDY PARTICIPANTS

9.1 Study Setting

Participants will have attended a heart failure clinic with a cardiology consultant at QAH between 01/01/2016-31/12/2016.

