9.3 Eligibility Criteria

Inclusion Criteria

The participant must meet ALL of the following criteria to be considered eligible for the study:

- Age 18-85yrs inclusive
- Currently or previously attended a heart failure clinic with a cardiology consultant at QAH
- Had an echocardiogram, ECG, BNP blood biomarker test in addition to a routine clinical evaluation (including age, weight and number of hypertensive medications) during January 1st 2016 – December 31st 2016.

Exclusion Criteria

The participant may not enter the study if ANY of the following apply:

- Known structural heart disease
- Significant heart valve disease (greater than mild stenosis, greater than moderate regurgitation)
- Pulmonary arterial hypertension
- Constrictive pericarditis
- Pre-existing cardiomyopathy
- Heart transplantation

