11.4 Study Assessments

All data will be collected retrospectively from the heart failure clinic database at QAH. Data will be collected on: weight, number of hypertensive medications prescribed, presence of AF or not, presence of pulmonary hypertension or not, age and filling pressure. These are the factors that make up Reddy et al. (2018) H2FPEF score. In addition the patient's ejection fraction and BNP will also be recorded as a measure to determine HFpEF diagnosis. All data will be anonymised and recorded on a Microsoft Excel spreadsheet, with a separate document documenting the pseudonymised data. All data will have been routinely collected as part of the heart failure patient pathway:

- Echocardiography - A non-invasive ultrasound test which takes approximately 30 minutes and has no radiation risk. Echocardiogram results will be used to ascertain pulmonary pressure and diastolic filling pressure. This will have been performed routinely as part of the heart failure patient pathway at QAH. All scans will have been performed on GE Healthcare Vivid echocardiography machines by a trained sonographer from the Cardiac Investigations Unit at QAH. A standard operating procedure exists for performing echocardiogram. In accordance with local practice personal protective equipment is worn for this test. ECG electrodes and ultrasound gel can be a potential risk to the patient with regards to dermatological reaction/sensitivity, however both are hypoallergenic substances.
- 12-lead electrocardiogram (ECG) - A non-invasive test of the electrical conduction of the heart assessing heart rate and rhythm. ECG results will be used to determine if the patient is in AF or not. All ECG will have been recorded with the use of the hospitals standard machine (MAC 1200, GE Healthcare). All tests will have been

performed by trained staff within the Cardiac Investigations Unit at QAH. Standard operating procedures are followed to perform ECG. ECG will have been performed routinely as part of the heart failure patient pathway at QAH.

- Weight - Using a standard trust scale (Marsden Weighing Company, UK)
- Age and Number of hypertensive medications taken - Assessed from patient records

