13.2 Analysis of Outcome Measures

To determine if the H2FPEF score was accurate in predicting HFpEF the calculated H2FPEF score will be compared against BNP blood test results using the cut-off points stated by the European Society of Cardiology (Ponikowski et al., 2016). To test our hypothesis an analysis of variance test (ANOVA) will be performed to provide one simultaneous evaluation of the data to determine if there is a significant difference between H2FPEF score and diagnosis of HFpEF. A logistic regression analysis will then be carried out to give an odds ratio and provide a predictive analysis of the data. All statistical analysis will be performed using SPSS software.

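### Specificity and overestimation are judged against low BNP cut-offs in a cohort from a BNP pathway clinic, with no check that enough reference-negative patients with EF ≥50% exist

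*Combined protocol and SAP*

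**What the plan says.** The study title (section 2) is "A retrospective observational analysis of a cohort with Heart Failure with Preserved Ejection Fraction from a BNP pathway clinic". Section 9.1 describes the setting differently: "Participants will have attended a heart failure clinic with a cardiology consultant at QAH between 01/01/2016-31/12/2016". Section 9.3 requires that each patient "Had an echocardiogram, ECG, BNP blood biomarker test in addition to a routine clinical evaluation" within 2016; it sets no minimum BNP and no EF limit. Section 10 takes every eligible patient. The synopsis plans 2000 patients, without a derivation.

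For the reference, section 13.2 says that "the calculated H2FPEF score will be compared against BNP blood test results using the cut-off points stated by the European Society of Cardiology". Section 5 lists, among the elements of initial diagnosis, "an elevated B-type natriuretic peptide (BNP) (>35 pg/mL", with NT-proBNP above 125 pg/mL as the alternative, together with signs and symptoms and EF of at least 50%. Section 11.4 adds: "In addition the patient's ejection fraction and BNP will also be recorded as a measure to determine HFpEF diagnosis".

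The primary outcome in section 8.2 is: "Accuracy of H2FPEF at predicting HFpEF on the patient population will be assessed as specificity and sensitivity". Section 7.2 makes overestimation relative to BNP a secondary objective, and the synopsis gives overestimation as the hypothesis. Under Impact, section 5 states that accepting the null hypothesis means the score has been validated locally and could be used by this and other trusts.

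**The concern.** Specificity and overestimation both depend on patients who are negative on the reference. The hypothesis is about over-diagnosis, so the informative negatives are patients with preserved EF who do not have heart failure. The clinic's name suggests that BNP may help decide who attends, and the same marker, at a low cut-off, then decides who counts as a case. If the two overlap strongly, informative negatives become scarce. The plan gives no BNP entry rule for the clinic, no expected number of negatives and no minimum below which specificity would not be interpreted.

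The risk is one-sided. When nearly everyone is reference-positive, even a score that over-diagnoses shows no excess of positives and a high positive predictive value. Section 5 would turn that result into a validation statement with consequences for practice.

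**Working it through.** **Inputs from the documents.** N = 2000 (synopsis). Cut-offs of BNP >35 or NT-proBNP >125 pg/mL (section 5). No alpha, power, prevalence, target specificity or precision is given, so the figure of 2000 cannot be reproduced.

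**Assumptions.** The share of the 2000 who are reference-negative with EF ≥50% is not given and is varied below. True specificity is set at 0.70 for illustration.

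**1. Precision of specificity.** Wilson 95% interval, with p = 0.70, z = 1.96 and n negatives:

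[p + z²/(2n) ± z·√(p(1−p)/n + z²/(4n²))] / (1 + z²/n)

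| Share negative | n | 95% CI |
|---|---|---|
| 0% | 0 | not estimable |
| 1% | 20 | 0.481 to 0.855 |
| 2% | 40 | 0.546 to 0.819 |
| 5% | 100 | 0.604 to 0.781 |
| 10% | 200 | 0.633 to 0.759 |
| 20% | 400 | 0.653 to 0.743 |

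**2. Negatives needed for a given half-width h.** n = z²·p(1−p)/h².
- h = 0.10: 3.84 × 0.21 / 0.01 = 80.7, so 81 (about 4% of 2000).
- h = 0.05: 3.84 × 0.21 / 0.0025 = 322.7, so 323 (about 16% of 2000).

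**3. Room for overestimation to appear.** With prevalence π, sensitivity se and specificity sp, the score-positive share is se·π + (1−sp)(1−π). Its excess over prevalence is (1−sp)(1−π) − (1−se)π, which can never exceed 1−π. Take se = 0.8 and sp = 0.7 (assumed):
- π = 0.50: share = 0.40 + 0.15 = 0.55; excess +5 points; positive predictive value 0.40/0.55 = 0.73.
- π = 0.95: share = 0.76 + 0.015 = 0.775; excess −17.5 points; positive predictive value 0.76/0.775 = 0.98. No score could show an excess above 5 points here.

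The excess is zero when 0.3(1−π) = 0.2π, that is, at π = 0.60. Above that prevalence, this score appears to underestimate, although it still labels 30% of the negatives as positive.

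**4. Does EF in the reference supply the negatives?** Suppose 10% to 50% of patients have EF <50% and 1% of the rest are below the BNP cut-off (assumed).
- 10%: 2000 × (1 − 0.90 × 0.99) = 218 negatives, of which 200 have EF <50% and 18 have EF ≥50%.
- 50%: 2000 × (1 − 0.50 × 0.99) = 1010 negatives, of which 1000 have EF <50% and 10 have EF ≥50%.

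The total becomes ample, but almost all of it consists of patients whom section 5 would class as reduced or mid-range EF. They do not test over-diagnosis among patients with preserved EF.

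**The case against.** The strongest objection is that selection on a raised BNP is not documented. Section 9.3 requires only that the test was done. The BNP pathway label appears once, in the title, and sections 9.1, 9.2 and 11 speak of heart failure clinics or their database. A reader might infer that raised BNP was an entry condition and that most reference-negatives are already lost. The documents do not support that; it is a reading of the clinic's name. A reader might also take the title to mean that every patient has HFpEF, but section 9 imposes no such restriction.

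The size can be overstated too. No source gives the share of negatives. At 5% the half-width is about 9 points, which is usable; serious imprecision begins at roughly 2% or below. It would also be wrong to say that no sample size could help, because at any fixed non-zero share the number of negatives grows with N.

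Finally, section 11.4 brings EF into the diagnosis, so specificity need not be undefined even if every patient has a raised BNP. This stands as to the number of non-cases. It does not answer whether they are the right non-cases, as step 4 shows.

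What remains after these objections is that the plan neither establishes nor checks the number of informative negatives, while section 5 draws a firm conclusion from a result that their absence would produce.

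**Conclusion.** The point holds conditionally. If entry depended on a raised BNP, or if few attenders with EF ≥50% fall below the cut-offs, specificity in the relevant group would range from imprecise (0.604 to 0.781 at 5% negatives, 0.481 to 0.855 at 1%) to not estimable (0%). Overestimation would be capped at 1 minus prevalence. The shares, the specificity of 0.70 and the sensitivity of 0.8 are assumptions; only N = 2000 and the cut-offs come from the documents.

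The documents do not support the stronger conclusion that the primary outcome and main hypothesis are already unanswerable. Nor do they require the consultant's diagnosis to become the primary reference. That diagnosis may have been made with BNP and echocardiography in view; pulmonary pressure and E/e' are components of the score, so the change would bring incorporation bias. No section confirms that a usable diagnosis is held in the database. The defect that can be shown is a validation rule with no condition on the evidence needed to contradict it.

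**What to change.** - **Section 13.2:** before any accuracy analysis, tabulate patients with EF ≥50% above and below the BNP cut-off, using the EF and BNP that section 11.4 says are recorded. The collection form in section 12.1 shows no column for either, so add both. Report specificity among EF ≥50% patients with its 95% CI.
- **Section 5, Impact:** replace the rule that accepting the null hypothesis amounts to validation. State that no specificity, overestimation or validation claim will be made from the BNP comparison unless a prespecified number of EF ≥50% reference-negatives is reached. At specificity 0.7, about 81 give ±10 points and 323 give ±5.
- **Section 9.1:** state the clinic's BNP entry rule. Limit the conclusion to patients referred with a raised BNP only if that rule is confirmed.
- **Optional:** if a clinic diagnosis is recorded, compare the score with it as a sensitivity analysis, without replacing the primary reference.

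The cost is a small tabulation, two columns on the form and some wording. The downside is that the permissible claim may be narrower.

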In response Reddy et al (2018) recently proposed non-invasive diagnostic criteria called H2FPEF which assesses patients based on body mass index (BMI), the number of hypertensive medications they take, presence of AF, pulmonary pressure, age and filling pressure. The advantage of the H2FPEF score is that it uses only non-invasive echocardiography data alongside routine clinical data making it easy to derive. However one key limitation of their study is the population they used was all from the Mayo clinic and so the generalisability of their results has not been tested for other populations, such as those of lower socioeconomic status like in Portsmouth. A further limitation is the parameters chosen to create H2FPEF are all relatively common morbidities and usually co-exist, making it likely that it will over diagnose HFpEF.

Research questions:

The main research question the investigators are investigating is whether the H2FPEF criteria proposed by Reddy et al. (2018) is an accurate predictor of HFpEF on the patient population at QAH. In the original paper by Reddy et al. (2018) they created and tested H2FPEF criteria on their study population from the Mayo clinic, Rochester, US. This population is predominantly Caucasian and of a high socioeconomic status and so lacks generalisability. In response the investigators are testing the H2FPEF criteria on the population at QAH which is of a lower socioeconomic status, to investigate if it remains an accurate predictor of HFpEF.

Risks:

As the investigators study is a retrospective observational study there are no risks to participants, and all data obtained will be anonymised with no personally identifiable data being analysed.

Impact:

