10. SAMPLING

All eligible participants between 01/01/2016 – 31/12/2016 will be included in the study. This is to allow sufficient time to be able to follow patient outcomes up. Outcomes such as any changes to medication and treatment as well as any hospital admissions and reported symptoms will be assessed. Including patients from 2016 will allow us to assess these outcomes one year after their clinic appointment.

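### Section 13.2 does not carry out the primary accuracy outcome: it names only an ANOVA and an odds ratio, which measure association, and no ROC area is planned

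*Combined protocol and SAP*

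**What the plan says.** The combined protocol and SAP describes the primary outcome in three places.

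- Synopsis, Primary Outcome Measure: "To assess the predictive accuracy of H2FPEF at predicting HFpEF on the patient population as calculated by logistic regression", and in the same sentence "with diagnostic accuracy being assessed by sensitivity and specificity calculations".
- Section 8.2: accuracy "will be assessed as specificity and sensitivity as calculated by logistic regression".
- Section 13.2: "To test our hypothesis an analysis of variance test (ANOVA) will be performed", comparing the score with the HFpEF diagnosis, and then "A logistic regression analysis will then be carried out to give an odds ratio and provide a predictive analysis of the data".

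Section 13.2 does not mention sensitivity or specificity and does not define the predictive analysis. No section gives a score or probability cut-off, an ROC area or c-statistic, a confidence interval, an acceptable level of accuracy, or a significance level. The question posed in section 5 is whether the score holds up in this population: "to investigate if it remains an accurate predictor of HFpEF".

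**The concern.** The primary question is about accuracy: how well the H2FPEF total separates patients with HFpEF from those without. The two procedures named in section 13.2 answer a different question, whether the score and the diagnosis are related at all. An odds ratio changes with its unit (per point, per category, over the whole range), and its p-value changes with the number of patients. Neither says how many patients the score classifies correctly.

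Sensitivity and specificity would answer the question. However, they need a cut-off on the 0-9 total, none is stated, and the analysis section does not pick them up. The measure that needs no cut-off, the ROC area, is not planned.

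This matters because section 5 (Impact) says that a favourable result would count as validation of the score, with possible use at this hospital and at other trusts. With no accuracy measure fixed in the analysis section, a clear association could be reported as though it were accuracy.

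**Working it through.** **The plan's own figure.** The synopsis gives "Planned Sample Size 2000". It cannot be reproduced, because the documents give no significance level, power, effect size, HFpEF prevalence or target precision. Section 10 takes every eligible patient ("All eligible participants between 01/01/2016 – 31/12/2016 will be included in the study"), so 2000 is an expected count.

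**Inputs from the documents.** n = 2000. Section 8.1 gives points of 2, 1, 3, 1, 1 and 1, so the total runs from 0 to 9.

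**Assumptions not in the documents.** The score is roughly normal in each group with equal SD; the within-group SD is 2 points; 10% to 50% are positive on the reference; the true ROC area is 0.53 to 0.60; tests are two-sided at 5%.

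**Formulas.** With A the ROC area and π the reference-positive fraction:

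- standardised difference d = √2 × Φ⁻¹(A)
- odds ratio per point = exp(d / SD)
- expected z = d × √(nπ(1 − π))
- sensitivity at 80% specificity = 1 − Φ(0.8416 − d)

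**Area 0.60.** d = 1.414 × 0.2533 = 0.358. Odds ratio per point = exp(0.358/2) = 1.20. Over all 9 points the same result is exp(9 × 0.179) = 5.0. Sensitivity at 80% specificity = 1 − Φ(0.483) = 31%. With SD 1.5 or 2.5 the odds ratio per point becomes 1.27 or 1.15 while the accuracy is unchanged.

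**Area 0.55.** d = 1.414 × 0.1257 = 0.178. Odds ratio per point = exp(0.178/2) = 1.09. Sensitivity at 80% specificity = 1 − Φ(0.664) = 25%.

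**Expected z and p at n = 2000.** These do not depend on the SD.

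| ROC area | 10% positive | 20% | 30% | 50% |
|---|---|---|---|---|
| 0.60 | 4.81, p = 1.5 × 10⁻⁶ | 6.41, 1.5 × 10⁻¹⁰ | 7.34, 2.1 × 10⁻¹³ | 8.01, 1.1 × 10⁻¹⁵ |
| 0.55 | 2.38, p = 0.017 | 3.18, 0.0015 | 3.64, 0.00027 | 3.97, 7.1 × 10⁻⁵ |
| 0.53 | 1.43, p = 0.15 | 1.90, 0.057 | 2.18, 0.029 | 2.38, 0.017 |

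For example, at area 0.60 and 50% positive, z = 0.358 × √500 = 8.01. Power at area 0.55 is 66, 89, 95 and 98% across the columns. If the diagnosis is treated as two groups, the ANOVA is the square of a two-sample t test. The same z then applies to it, so it adds little that the odds ratio does not already show.

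**Check on a discrete score.** Totals were simulated with the section 8.1 points and assumed item frequencies (400 runs per setting; 20, 30 and 50% positive). With a mean area of about 0.557, the odds ratio was 1.11 per point and p < 0.05 in 95% to 99.5% of runs. With about 0.544, it was 1.08 and 80% to 94%. The normal approximation is not driving the result.

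**What n = 2000 gives on accuracy measures.** By the Hanley-McNeil formula at area 0.60 and 50% positive, the variance is [0.24 + 999 × 0.0686 + 999 × 0.09] / 10⁶ = 1.59 × 10⁻⁴. The standard error is 0.0126 and the 95% half-width 0.025. At 20% or 80% positive the half-width is about 0.03. For sensitivity, with an assumed true value of 0.80, the half-width is 1.96 × √(0.16 / (2000π)), which is 5.5, 3.9, 3.2 and 2.5 percentage points at 10, 20, 30 and 50% positive. The planned number is adequate for estimating accuracy; what is missing is the specification.

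**The case against.** The strongest reply is that accuracy measures are in the plan. The synopsis and section 8.2 both name sensitivity and specificity, and section 8.2 attaches them to the logistic regression. A reader of section 13.2 alone might infer that the odds ratio is the only statistic the regression is meant to yield; the document as a whole does not support that. A team following all three sections would try to report sensitivity and specificity, and a score with 31% sensitivity at 80% specificity would look weak whatever its p-value. This stands, and it limits the point to what section 13.2 leaves out. It does not close the gap, because without a cut-off the two measures cannot be calculated, and the analysis section never says that they will be.

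A reader might also infer that a significant odds ratio is the plan's test of success. No section says so. The hypothesis test named in section 13.2 is the ANOVA, no significance level is stated, and no section proposes quoting the odds ratio over the full 0-9 range.

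A third inference would be that any poor score comes out highly significant at n = 2000. That depends on assumed values. At area 0.55 with 10% positive, p is only about 0.017 with 66% power. At area 0.53, power is 30% to 66%. The eligible number may also fall short of 2000; at area 0.60 with n = 1000 and 50% positive, p is about 1.5 × 10⁻⁸.

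Finally, the ROC area depends only on ranking. It would not change if every predicted probability were too high, so it cannot test the synopsis hypothesis that the score overestimates HFpEF. That is correct, and the fix has to say so.

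**Conclusion.** The point holds as a gap between the stated primary outcome and the analysis section. The synopsis and section 8.2 promise accuracy; section 13.2 names an ANOVA and an odds ratio, which measure association. Sensitivity and specificity are named elsewhere but lack a cut-off and are not carried through, and no cut-off-free measure of discrimination is planned.

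That the named procedures measure association needs no assumption. The size of the possible mismatch does: under the normal model with n = 2000, weak discrimination (area 0.60) would accompany p-values far below 0.001 across 10% to 50% positive, and area 0.55 would usually, though not always, reach p < 0.05. A significant odds ratio is therefore compatible with poor accuracy. The documents do not show that the primary outcome rests on the odds ratio alone, or that its significance would be taken as success.

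**What to change.** 1. In the synopsis, section 8.2 and section 13.2, define predictive accuracy as the area under the ROC curve of the unchanged 0-9 H2FPEF total, with a 95% confidence interval (DeLong).
2. Carry sensitivity and specificity of the unchanged score into section 13.2 with 95% confidence intervals, either at every possible score cut-off or at one that the investigators name before analysis.
3. Report the odds ratio per point as descriptive, and state that neither it nor its p-value is evidence of accuracy.
4. State that the ROC area does not address overestimation. That hypothesis needs its own comparison of predicted with observed HFpEF frequency. The documents give points but no conversion from score to probability, so the source of the predicted values must also be stated.

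Items 1 to 3 cost wording in three places and one extra procedure on data already planned, with no new patients or variables. Item 4 adds a second comparison on the same patients. The drawback is that the reported result may look less favourable than a significant odds ratio.
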